- Stepped care models paired with accurate risk identification can reach priority adolescents without increasing burden on the health system. There are great concerns about the capacity of health systems to manage care in the ‘Test and Start’ era. Stepped care models use programmatic data to target services to those most in need. This framework is highly aligned with international movements for differentiated care.
- Current Kenyan guidelines for differentiated care do not include adolescents. All HIV-infected adolescents are considered “unstable” and thus not eligible for differentiated HIV services under current Kenyan guidelines.[49] This approach masks heterogeneity and diverse needs. Carefully and systematically assessing individual risk can identify those who need heightened services, as well as those at lower risk, who may benefit from less intensive or frequent clinic visits according to differentiated care models.
- A health systems intervention can be widely applied across different settings. Despite national roll out of the Adolescent Package of Care (APoC) guidelines, large scale and local programs targeting adolescents with HIV are not uniform. A health systems approach can be applied across clinical facilities to enhance diverse interventions by matching them to client characteristics and specific health system compositions.
- Client-centered interventions that involve providers, families, and youth in design and implementation can maximize uptake and impact. Youth perspectives are critical to engagement in HIV research and programs and to determine what additional support might be needed.[69] Addressing legal and ethical considerations can maximize representative participation and better inform design and delivery.
- Effectiveness research is necessary to develop sustainable models for adolescent HIV care: We will evaluate the DiSC intervention by leveraging routine electronic medical record (EMR) data and clinic populations and engaging community stakeholders throughout the study lifecycle. By approximating real-world conditions, we maximize generalizability and sustainability of this model in resource-limited settings.[70]
- Using an implementation-effectiveness hybrid design improves translation to practice: Our study is structured *a priori* to address both clinical intervention and implementation outcomes. Use of hybrid study designs may improve policy relevance and public health impact of new interventions.[71]

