4.1 OVERALL DESIGN

In aim 1, with relevant stakeholders in adolescent HIV, we will collaboratively develop the DiSC intervention, then adapt and pilot test the intervention.

In aim 2, we will conduct a cluster randomized trial (cRCT) in up to 24 sites in western Kenya (12 randomized to intervention and 12 to control) (Figure 1).

Figure 1: Study design, main activities, and outcomes

Adapted from NIH Behavioral and Social Intervention Clinical Trial Protocol Template v3.0 - 20180827

Study hypothesis

- Primary and secondary outcomes: We hypothesize that the DiSC intervention will result in better retention, adherence and viral suppression among adolescents in the intervention sites compare to those in control sites. Hypothesized psychosocial outcomes will include better psychosocial and family support, mental health, family support and adolescent self-efficacy.
- We hypothesize the DiSC intervention will be associated with improved clinic efficiency (client wait time), and will be cost effective.
- The DiSC Intervention will be feasible, acceptable to HCW and adolescents but will require clinic specific intervention adaptations.

Randomization

Up to 24 clinics will be randomized in a 1:1 ratio using computer generated random numbers to either intervention or control, using restricted randomization to balance by county, aiming to balance the numbers of clinics from each county between arms. Timing of randomization will be prior to study start. Randomization will be done at the University of Washington by a biostatistician not involved in study procedures. A list of clinics with their allocation arms will be sent to the study team. We will perform individual substitutions of sites on a case by case basis, as needed (e.g. if the site no longer meets an eligibility criterion). The intervention is administered at the clinic-level; it is not possible to blind participating clinics or study team members.

Study intervention

The DiSC intervention is comprised of a system to assign adolescents to care based on their health needs and the different levels of care for each assignment group. Control sites will continue with standard of care approaches for adolescent clinic visits (usually 1-3 monthly visits) regardless of health care needs and additional support as needed.

Analysis

Adapted from NIH Behavioral and Social Intervention Clinical Trial Protocol Template v3.0 - 20180827

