6 STUDY INTERVENTION(S) OR EXPERIMENTAL MANIPULATION(S)

6.1 STUDY INTERVENTION(S) OR EXPERIMENTAL MANIPULATION(S) ADMINISTRATION

6.1.1 STUDY INTERVENTION OR EXPERIMENTAL MANIPULATION DESCRIPTION

The Data-informed Stepped Care (DiSC) intervention is comprised of a system to assign ALHIV to different levels of care, or “steps”, depending on their current and anticipated health care needs. Stepped care is a model grounded in Stages of Change Theory and has been used in mental health fields to organize provision of services, and to support clients, HCWs, and caregivers to identify interventions tailored to individual need. HCWs at participating sites will assign ALHIV to different levels or intensity of HIV services. The trajectory of services moves from a relative position of ALHIV autonomy to more intensive service provision. Intervention steps could start with multi-month refills or community treatment delivery, then social support activities (support groups, life skills activities), progress to individualized services (text messaging, ‘big brother/sister’ older peer support, motivational interviewing), and ultimately a case management approach involving referrals to specialized care like mental health or gender-based violence services, individualized counseling, and active tracking of individual participation in support and care services. The stepped care framework is designed to be flexible, to accommodate variable

Adapted from NIH Behavioral and Social Intervention Clinical Trial Protocol Template v3.0 - 20180827

individual and social support services available at each facility. A sample of potential intervention steps is presented below:

Sample intervention steps

Levels	Criteria for eligibility	Regular care	Additional HCW provided	Additional clinic recommended
Stepped down care	Meets MoH criteria except age	-Differentiated care	None	-Support groups (optional)
Not retained	At risk for loss	-3 monthly visits	-Pre-clinic reminders (text) -Individual peer support -3 monthly adherence counseling	-Support group
Viral failure	At risk for viral failure OR VL under 1000 but detectable	-Monthly visits (6 weekly for school going)	-Monthly adherence counseling -Motivational interviewing (one round of several sessions) OR Coaching -Individualized ART pick-up strategies	-Support group -Caregiver or support person DOTS

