Failed	Unsuppressed at last measure	-Monthly visits (6 weekly for school going)	-2 weekly adherence sessions (could make some on phone) -Accelerated repeat test timeline (3 month) -Prompt switch after second test -Case manager -DOTS by HCW (or caregiver/family)	-Support group -Special treatment failure support groups -Home visit by HCW -Viremia clinics

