2.1. Summary of primary and secondary outcomes

Table 1. Outcome definitions and assessment

Outcome	Indicator	Source	Timing
Primary outcome			
Retention in care	Missed visits: Not seen within 30 days of a scheduled visit.	EMR data (Visit Date, TCA)	All visits occurring during the 12-month period after the study enrollment visit*
Secondary outcomes			
Loss to follow-up	Not return to care within the 12 months study interval	EMR data (Visit Date, TCA)	All visits after the first study visit until event or end of follow-up at 12 months. Participants marked as 'transferred out' or 'died' will be censored.
Viral non-suppression	Having HIV viral load (VL) >1,000 copies/mL	NASCOP data, abstraction of paper records	All visits from enrollment to 12 months follow-up*
Receiving differentiated care	
 Long inter-visit interval Fast-track visit 	EMR data (TCA, Care Model)	All visits from enrollment to 12 months follow-up*
Adherence	Pill coverage estimated by days of dosing and inter-visit interval since last visit >80%	EMR data (Visit Date, next Visit Date, Duration)	All visits from enrollment to 12 months follow-up*

*time window up to 12 months + 30 days

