3.4. Analysis of retention

Retention will be evaluated using an indicator of missed visits. A missed visit will be defined as a participant not seen within 30 days of a scheduled visit during follow-up since the first stepped care visit to 12 months. Each scheduled visit will be classified as missed versus not missed and analysis will use repeated measures per participant. The proportion of missed visits will be compared between study arms using mixed-effects Poisson regression with random effects for facility and participant and robust standard errors.

Sub-group analyses for retention will be performed by gender and age-group. Facility factors, including concurrent adolescent-friendly services and high/low performance will be evaluated as modifiers of intervention effectiveness.

Table 4. Analysis of missed visits

	Overall	Control	Intervention	Intervention vs. control
Missed visits per participant				^a RR (95% CI)
Median (IQR)				
Number of scheduled visits				
Number of missed visits (%)				
Missed visits over all participants				
Count (proportion)				
Number of scheduled visits				
Number of missed visits (%)				
Number of AYA ever missed a visit (%)				

^a Estimated by mixed-effects Poisson regression with random effects for facility and participant and robust standard errors

*Excluding TCA that had miss/no-miss status censored or missing

*Models adjusted for any factors differing between arm with statistical significance at enrollment

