3.5. Analysis of secondary study outcomes

3.5.1. Loss to follow-up:

- Loss to follow-up will be defined as a participant missed a visit and did not return to care within the 12-month study period. The proportion of loss to follow-up during 12-month study interval (window up to 12 months +30 days) will be compared between study arms using Poisson regression with robust errors.
- Time to loss to follow-up will be compared between arms by survival curves, and death or transfers will be censored. The hazard of loss to follow-up will be compared between study arms using Cox proportional hazards regression.

3.5.2. Viral non-suppression:

- Viral non-suppression will be defined as having HIV viral loads (VL) >1,000 copies/mL. Each VL testing result will be classified as VL suppressed vs. unsuppressed. The proportion of viral non-suppression during follow-up will be compared between study arms using mixed-effects Poisson regression with random effects for facility and participant and robust standard errors.

3.5.3. Receiving differentiated care:

- Receiving differentiated care will be defined in two ways. One approach will evaluate the next visit appointment date (scheduled inter-visit interval) – visits scheduled for ≥ 3 months after visit will be considered as differentiated care, in comparison to monthly visits recommended for AYA in current guidelines. The second approach will use the variable ‘fast-track’ at each visit – ‘fast track’ visits are considered as a component of differentiated care. Two analyses will be conducted (one for long scheduled inter-visit interval and one for ‘fast track’), each will be compared between study arms using mixed-effects Poisson regression with random effects for facility and participant and robust standard errors.

3.5.4. Adherence:

- Adherence will be evaluated using the proportion of days of pill dosing over days of inter-visit interval. The level of adherence during the past inter-visit interval will be assessed at each visit. A proportion over 80% as good adherence. The dichotomized adherence will be compared between arms using mixed-effects Poisson regression with random effects for facility and participant and robust standard errors.

Table 5. Analysis of secondary study outcomes

Loss to follow-up				
	Overall	Control	Intervention	Intervention vs. control
	Count (proportion)			^a RR (95% CI) ^b HR (95% CI)
Event Person-year Cumulative incidence Incidence rate (per 100 person-years)				
Viral non-suppression				

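### The SAP's 80% power is for participant-level retention, not for its per-visit primary outcome, and the documents state that primary outcome in four different ways

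*SAP*

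**What the plan says.** **The primary outcome appears in four forms.**
- Protocol 1.1 (synopsis): the percentage of participants retained at 6 and at 12 months.
- Protocol 8.1 (outcome table): being more than 30 days late for an appointment, assessed six-monthly.
- Protocol 9.4.2: the number of missed visits, in a mixed model.
- SAP 2.1 and 3.4: "Missed visits: Not seen within 30 days of a scheduled visit", over all visits in 12 months. "Each scheduled visit will be classified as missed versus not missed and analysis will use repeated measures per participant". The proportion missed is compared by mixed-effects Poisson regression with facility and participant random effects.

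**Power.** SAP 2.2.1 assumes 75% of participants in care at 12 months in the control arm. With 12 facilities per arm it claims 80% power for 75% v 89% (150 participants per facility, 0.10).

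**Visit schedule.** Protocol 2.2 foresees a group of "those at lower risk, who may benefit from less intensive or frequent clinic visits according to differentiated care models". Protocol 6.1.1 says "Intervention steps could start with multi-month refills or community treatment delivery", while two of its sample steps carry "Monthly visits (6 weekly for school going". Protocol 4.1 says "Control sites will continue with standard of care approaches for adolescent clinic visits (usually 1-3 monthly visits) regardless of health care needs". SAP 3.5.3 compares interval length between arms: appointments set three or more months ahead "will be considered as differentiated care, in comparison to monthly visits recommended for AYA in current guidelines". The primary model adjusts only for factors that differ at enrollment.

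**Loss to follow-up.** This is secondary in SAP 3.5.1. The proportion lost "will be compared between study arms using Poisson regression with robust errors", and time to loss by Cox regression. Neither model names facility, although the models for the other secondary outcomes have a facility random effect.

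**The concern.** Three things are at stake. First, a reader cannot tell which quantity answers the primary objective. The percentage retained at a time point, a count of missed visits and a proportion of appointments missed are different estimands and can give different answers. Second, the 80% power belongs to one of these and the primary test to another. Third, the denominator of the primary RR is fixed after randomization by a process the intervention may alter. A change in appointment spacing could then move the RR without any change in retention, or leave it still while retention changes. The natural cross-check, participant-level loss, has models that do not state the facility clustering they need in a cluster-randomized trial.

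**Working it through.** **1. Reproduce the SAP's figure.** Inputs from SAP 2.2: 75% v 89%, 150 participants per facility, 0.10 used as an intraclass correlation, 80% power, alpha 0.05 (two-sided reproduces).

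Facilities per arm = 7.849 × [p1(1−p1) + p2(1−p2)] × [1 + (m−1) × ICC] / [m × (p1−p2)²]
= 7.849 × (0.1875 + 0.0979) × (1 + 149 × 0.10) / (150 × 0.14²) = 12.1; the table shows 12.

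Power at 12 per arm: effective n = 12 × 150 / 15.9 = 113.2, and Φ(0.14 / √(0.2854/113.2) − 1.96) = 79.6%.

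The formula matches 70 of the table's 72 retention cells exactly; the other two differ by one through rounding. It uses one binary outcome per participant. Nothing in it refers to visits.

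**2. Can the documents give power for the per-visit RR?** No. A missed-visit rate, visits per person and a within-person correlation are all absent.

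**3. Illustration: equal retention, changed schedule.** These assumptions are not in the documents. Controls are half monthly and half 3-monthly. Loss runs at a constant calendar rate to R = 75% at 12 months. Each lost person leaves one missed appointment. q is the risk of a temporary miss per appointment. With n visits a year, p = 1 − R^(1/n) and expected scheduled visits S = (1−R)/p, which is 10.554 (monthly) or 3.603 (3-monthly). Proportion missed = [(1−R) + q(S − (1−R))] / S, with S averaged over the mix.

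Average S is 7.08 at a 50% 3-monthly share, 5.34 at 75% and 8.82 at 25%. At q = 0 the RR is 7.08/5.34 = 1.33 if the share rises 25 points.

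| 3-monthly share | q = 0 | q = 5% | q = 12% |
|---|---|---|---|
| up 25 points | 1.33 | 1.13 | 1.07 |
| no change | 1 | 1 | 1 |
| down 25 points | 0.80 | 0.92 | 0.96 |

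**4. The opposite model.** If the miss risk is constant per appointment (0.0237), 75% are retained on monthly and 90.9% on 3-monthly visits. A 25-point rise in the 3-monthly share gives 82.9% v 86.9% retained while the visit RR stays at 1.

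**5. Is participant-level loss schedule-free?** Simulation with 200,000 people per schedule, 25% loss, random appointment phase, temporary gaps of 2–3 months and the 12 months + 30 days rule:

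| 25-point shift | RR | q = 0 | q = 5% | q = 12% |
|---|---|---|---|---|
| longer intervals | visit | 1.30 | 1.11 | 1.06 |
| longer intervals | loss | 0.98 | 0.95 | 0.93 |
| shorter intervals | loss | 1.02 | 1.05 | 1.07 |

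With longer intervals, fewer people have shown a missed appointment by the cut-off. At q = 12% loss depends on the schedule slightly more than the visit RR does. Looking back from month 18 brings the loss RR to 1.01–1.02 (longer) or 0.98–0.99 (shorter).

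**6. Illustrative power for 75% v 89%.** 3,000 runs, 12 clinics × 150 per arm, ICC 0.10, log ratio with clinic-robust variance and t on 22 df. This is not the SAP's mixed model. Participant-level power is 72–75%. Per visit, at q = 0, 5%, 12%:
- no shift: 75%, 73%, 62%
- longer intervals: 42%, 43%, 36%
- shorter intervals: 90%, 87%, 81%

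If q also varies between clinics (assumed SD 2 points at 5%, 4 points at 12%), no-shift power is 41% and 16%. With equal retention, rejection is 5–6% (no shift), 7–17% (longer) and 6–13% (shorter).

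**The case against.** The SAP did not invent the per-visit measure: protocol 9.4.2 already compares missed visits and the outcome table already uses lateness, so the synopsis could be called the outlier. The steps in protocol 6.1.1 are samples that move visits in both directions, and protocol 4.3 describes visits as typically 1 to 6 months apart. No net shift is therefore specified, and the 25-point shift and 50/50 control mix are invented. Loss to follow-up is planned, and SAP Tables 4 and 5 report scheduled visits and long intervals by arm. The outcome is built from visit and appointment dates, which suggests one missed appointment after loss, as assumed above. The robust errors in the loss model might be facility-clustered.

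Most of this stands, and it limits the point. It does not remove the four definitions, the mismatch between power and primary analysis, or the missing statement on clustering; all three hold with no schedule shift.

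A reader might infer more: that the primary analysis is biased against DiSC, or will hide a real retention gain. The documents do not support that. The sign depends on an unknown shift and on which loss model is true. Even with longer intervals, the illustrative visit RRs for 75% v 89% are 0.55, 0.82 and 0.91, weaker but still favouring DiSC. Nor can one conclude that participant-level retention is the unbiased choice, given step 5.

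**Conclusion.** The primary outcome is stated inconsistently, and the stated 80% power is for participant-level retention and not for the per-visit RR. Both findings rest on the text and on the reproduced formula, without added assumptions. True power for the per-visit RR cannot be derived from the documents.

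The per-visit RR and 12-month retention can diverge if DiSC changes the schedule. Whether and which way they will is unknown, and the net shift may be zero. The ranges of 0.80–1.33 for the visit RR and 0.93–1.07 for loss, and all simulated power figures, are illustrations on assumed schedules and miss risks. The missing facility term in the loss models is a separate, definite gap: analysed as written, loss to follow-up could be tested as though participants within a clinic were independent.

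**What to change.** Before database lock, from the same EMR data:

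1. Reconcile protocol 1.1, 8.1 and 9.4.2 with SAP 2.1, 2.2.1 and 3.4 on one primary estimand.
2. *If missed visits stay primary*, state that the SAP 2.2 power is for participant-level retention, or recompute it for the per-visit outcome with stated miss rates, visits per person and correlations. Interpret the RR beside participant-level 12-month retention and the scheduled visits and intervals by arm.
   *If participant-level retention becomes primary*, the existing calculation applies (about 80% by its normal formula, 72–75% in the simulation above). Disclose that this measure also depends on the interval. Add a longer look-back as a sensitivity analysis only if later EMR data are abstracted: the synopsis and protocol 9.4.3 list 18 and 24 months, but protocol 4.4 ends the study at the 12-month assessment.
3. Account for facility clustering, with a small-sample correction, in the loss to follow-up Poisson and Cox models.

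The cost is wording in both documents and a little analysis. No new data are needed for the primary result. Using one record per participant loses little: in the SAP's own table, 75% v 89% at 0.10 needs 12 facilities per arm with 200 participants each and 14 with 50.

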1.2 SCHEMA

1.3 SCHEDULE OF ACTIVITIES

	Outcome assessed	Pre-screening (Pre-consent)	Enrollment	Enrollment Month 0±2	Month 6 Month 6±2	Month 12 Month 12±2	Unscheduled Visits
Clinic Eligibility		X					
Aim 2							
EMR data abstractions	Retention, viral non suppression		X	X	X	X	
Informed Consent (surveys)	NA		X				
Caregiver/adolescent surveys	Secondary outcomes		X		X	X	
HCW surveys	Health service & Implementation outcomes		X			X	
HCW implementation logs/surveys	Implementation outcomes						X
HCW implementation surveys, IDI /FGD (intervention sites only)	Implementation outcomes				X		
Facility surveys	Implementation outcomes		X			X	
Adolescent/caregiver satisfaction surveys (intervention only)	Implementation outcomes					X	
Adolescent FGDs	Implementation outcomes						
Randomization	NA	X					

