Program records: We will abstract ALHIV medical record data at baseline and regular intervals throughout the study. Data from all adolescents with at least 1 clinic record within the 12-month period prior to the first data abstraction date will be included. Data will be abstracted at the facility or at the office of the technical partner that supports the EMR system at the facility. The EMR system captures data on client anthropometric measures, demographics, HIV testing history, family members, clinical history, ART adherence data, laboratory data, CD4 count, transfers, and discontinuations. Routine viral load testing (done 6 months after ART initiation, then annually) will be abstracted from the EMR, if available, or NASCOP's laboratory database. If EMR data is unavailable, paper medical records will be abstracted using mobile REDCap which enables automatic upload of data to a secure, password-protected study server.

Adolescent behavioral surveys: Adolescent surveys will include questions on socio-demographics, health care use, stigma, sexual behavior, psychosocial support, mental health, personal health knowledge, HIV disclosure and medication adherence. Surveys will be administered every 6 months either in-person or over phone by a trained study staff. Survey visits will coincide with clinic visits as much as possible.

Caregiver behavioral surveys: Caregiver surveys will include questions on socio-demographics and family, caregiver roles, HIV disclosure, HIV care experience, disclosure, social support, mental health, HIV testing and awareness, personal health and HIV experience, HIV stigma, ART knowledge and adherence. Surveys will be administered every 12 months either in-person or over phone by a trained study staff. Survey visits will coincide with clinic visits as much as possible.

Data on health services and implementation outcomes will be collected as previously described (see section 6.2).

To track implementation, the following surveys will be conducted:

Facility surveys: Facility managers will complete baseline and annual facility surveys to understand baseline resource capacity to implement future interventions and modifiable and non-modifiable health system factors. Variables will include availability of youth-friendly services, management and referral systems, and differentiated care services available.

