2.2. Sample size considerations

2.2.1. Sample size and power for primary outcome

In our sample of HIV care facilities with >1,000 clients enrolled overall, we anticipate at least 10% will be eligible adolescents and young adults (AYA), with about 100-200 AYA per clinic on average. Based on our UG3 data, we assume that 75% will be in care (not LTFU) by the end of 12-month follow-up period. Given a minimum of 24 facilities in the trial (minimum 12 per arm), we estimated the minimum average number of AYA per facility to detect a 14-18% point change in retention using EMR data. Assuming 12 facilities per arm, 80% power, $\alpha=0.05$ and coefficient of variation of 0.10 (Table 2), we can detect a 14%-point difference (75% to 89%) with at least 150 AYA per facility, and a 15%-point difference (75% to 90%) with at least 50 AYA per facility. Assuming coefficient of variation of 0.15, we can detect a 17%-point difference (75% to 92%) with at least 50 AYA per facility (Table 2). Detecting a less than 14%-point difference or if assuming a larger correlation coefficient of individuals within a facility would require more participants per facility or more facilities per arm.

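### SAP 3.4 does not prespecify the clinic's pre-trial missed-visit rate as a covariate; the precision forgone depends on a between-year correlation the documents do not give

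*SAP*

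**What the plan says.** **Outcome and model.** SAP 2.1 defines the primary outcome as "Missed visits: Not seen within 30 days of a scheduled visit", taken from the EMR fields Visit Date and TCA. SAP 3.4 then says: "The proportion of missed visits will be compared between study arms using mixed-effects Poisson regression with random effects for facility and participant", with robust standard errors. No covariate is named.

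**Adjustment.** A footnote to SAP Table 4 reads: "Models adjusted for any factors differing between arm with statistical significance at enrollment". Table 3 in SAP 3.3, the list of baseline characteristics, has no earlier missed visits and no viral load. Clinic performance appears once, as an undefined moderator: "Facility factors, including concurrent adolescent-friendly services and high/low performance will be evaluated as modifiers of intervention effectiveness". That examines whether the effect varies; it does not adjust the main comparison.

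**Design.** Protocol 4.1 restricts randomisation on county only, so clinics are not balanced on earlier retention.

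**Baseline data.** Protocol 8.1 says "We will abstract ALHIV medical record data at baseline and regular intervals throughout the study" and "Data from all adolescents with at least 1 clinic record within the 12-month period prior to the first data abstraction date will be included". In Protocol 1.3 the EMR abstraction row, whose purpose is given as "Retention, viral non suppression", is also marked at enrollment.

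**The concern.** The trial has 24 clinics. At the between-clinic variation the SAP assumes, almost all the uncertainty in the arm comparison comes from differences among clinics, and more participants per clinic hardly reduce it. The SAP's own table shows this: for 75% against 89%, both 150 and 200 adolescents and young adults (AYA) per clinic need 12 clinics per arm.

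A clinic's missed-visit rate in the year before the trial is an obvious candidate to explain part of those differences. It is measured before allocation, so the intervention cannot affect it. Without it in the model, chance imbalance in clinic performance stays in the arm contrast and in the error term. The footnote does not fill the gap. Whether the variable enters would depend on a significance test after allocation, and the variable is not on the list of baseline characteristics.

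**Working it through.** **Inputs.** From SAP 2.2.1 and its table: 12 clinics per arm, m = 150 AYA per clinic, 75% against 89% retained, alpha 0.05 (taken as two-sided), 80% power, between-clinic variation 0.10. The text calls 0.10 a coefficient of variation and the table header calls it an ICC. Read as an ICC, the formula below matches 70 of the 72 retention cells exactly and the other two within 1, so it is used as an ICC here.

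**1. The plan's own figure.**
- Design effect = 1 + (150 − 1) × 0.10 = 15.9.
- Clinics per arm = (z₀.₉₇₅ + z₀.₈₀)² × [p₁(1−p₁) + p₂(1−p₂)] × design effect / (m d²) = 7.849 × (0.1875 + 0.0979) × 15.9 / (150 × 0.14²) = 12.11. The SAP table gives 12.
- At 12 per arm, SE = √(0.2854 × 0.106 / 12) = 0.0502, where 0.106 = 15.9/150. Power = Φ(0.14/0.0502 − 1.96) = 79.6%. With a t reference on 22 degrees of freedom it is 76%.

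No covariate is assumed anywhere in this.

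**2. Where the variance lies.** The variance of a clinic's proportion is proportional to ICC + (1 − ICC)/m = 0.10 + 0.006 = 0.106. The between-clinic share is 0.10/0.106, about 94%.

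**3. Effect of a clinic-level baseline covariate.** If r is the correlation between a clinic's baseline and follow-up proportions, adjustment multiplies the variance of the contrast by about (1 − r²) and costs one degree of freedom (21 instead of 22). **No document gives r; every value below is an assumption.** For example, at r = 0.5, SE = 0.0502 × √0.75 = 0.0435 and power = Φ(0.14/0.0435 − 1.96) = 89.6%.

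The simulation used beta-distributed clinic proportions with ICC 0.10, correlated baseline and follow-up years, and binomial sampling of 150 per clinic. It compared a clinic-level t test with clinic-level ANCOVA.

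| Case | Formula, normal | Formula, t | Simulation | Detectable difference at 80% power (normal) |
|---|---|---|---|---|
| No covariate | 79.6% | 76% | 76-77% | 14.1 points |
| r = 0 | – | – | about 75% | – |
| r = 0.3 | 83% | 78% | 78% | 13.5 |
| r = 0.5 | 90% | 85% | 84% | 12.4 |
| r = 0.7 | 97% | 95% | 93% | 10.5 |
| r = 0.8 | over 99% | 99% | 97% | 9.0 |

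The simulation is slightly less optimistic at higher r. Its r describes the underlying clinic rates, and the correlation between observed proportions is lower (about 0.46 for an input of 0.5 and 0.63 for 0.7). The simulated figures are the ones to rely on. Type I error of the adjusted clinic-level analysis was 4.6%.

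**4. Whether the data exist.** The outcome needs only Visit Date and TCA. Protocol 8.1 provides a baseline abstraction and admits anyone with a record in the preceding 12 months. It states who is included, not that a full year of past visit and appointment dates is extracted, and it counts back from the first abstraction date rather than from randomisation. Derivation is very likely possible, but it is an inference.

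**The case against.** The strongest reply is that nothing here is an error. The 80% was calculated without covariates and reproduces, so the plan does not miss its own target by leaving one out. A reader might infer that the omission makes the trial underpowered; the documents do not support that. The step from 79.6% to 76-77% comes from using a t reference with 24 clinics, not from the missing covariate.

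A reader might also infer that a large amount of power is certainly being given up. That rests on r, which is not stated. At 0.3 the gain is about 1 point in simulation, and at 0 there is a loss of about 2 points. This objection stands, and it limits the claim.

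Three further objections stand in part:
- The power figures are for the proportion in care at 12 months, which is the SAP's sizing basis. The primary analysis is of repeated missed visits, for which no base rate is stated.
- The simulated analysis is clinic-level ANCOVA with t inference, not the planned Poisson model, for which the SAP states no small-sample correction. As a stand-in, a marginal Poisson model with cluster-robust z tests on 24 clinics gave type I error of 7-8% unadjusted and 8-9% adjusted. The 4.6% therefore cannot be carried over to the planned model.
- The footnote refers to any factor, so it would be too strong to say that baseline performance is barred from the model. It could enter, but only through a data-driven rule, which is not a prespecified adjustment.

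What survives is the asymmetry. A covariate that proves useless costs about 2 points of power; at r of 0.5 to 0.8 it returns roughly 7 to 20.

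**Conclusion.** The point holds as forgone precision. SAP 3.4 prespecifies no baseline value of the primary outcome, although the baseline abstraction very likely supplies one and between-clinic variance dominates.

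In the sizing case, power moves from about 77% to about 75%, 78%, 84%, 93% and 97% at r = 0, 0.3, 0.5, 0.7 and 0.8. The gain is large only from about r = 0.6-0.7.

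This rests on reading 0.10 as an ICC, on assumed values of r, on participant-level retention standing in for missed visits, and on clinic-level t inference. Missed-visit figures may differ. The sponsor may be able to estimate r from the earlier-phase (UG3) data, which already supplied the 75%.

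**What to change.** In SAP 3.4:
- Prespecify each clinic's missed-visit proportion over the 12 months before randomisation, using the same 30-day rule, as a covariate in the primary model. Let this replace the significance-based footnote.
- Confirm that the baseline extract holds prior-year Visit Date and TCA back to 12 months before randomisation; if not, widen the extract.
- State inference suited to 24 clusters: a t reference with clinic-level degrees of freedom, or another small-sample correction.
- Keep the unadjusted estimate as supportive, and add the baseline missed-visit proportion to Table 3.

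Optional additions, whose gain was not computed, are the participant's own prior-year visit history in 3.4 and the last pre-enrollment viral load in 3.5.2.

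Cost: SAP wording, one derived variable, one clinic-level degree of freedom of 22, and about 2 points of power if the covariate turns out to be uninformative.
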